### 6.7.6 Management of Noninfectious Pneumonitis

Guidance for the management of pneumonitis is provided in [Table 6-6](#).

**Table 6-6 Management of Noninfectious Pneumonitis**

Grade	Description	Treatment	MLN0128 Dose Modification
1	Asymptomatic: Radiographic findings only	Rule out infection and closely monitor	None
2	Symptomatic: Not interfering with activities of daily living	Rule out infection and consider treatment with corticosteroids until symptoms improve to $\leq$ Grade 1.	Interrupt MLN0128 treatment: 
 
When symptoms <math>\leq</math>Grade 1, reinitiate MLN0128 treatment with a dose reduction. (a)
 
If no recovery within 4 weeks, then discontinue MLN0128 treatment.
 

3	Symptomatic: Interfering with activities of daily living Requires administration of oxygen	Rule out infection and consider treatment with corticosteroids until symptoms improve to $\leq$ Grade 1.	Interrupt MLN0128 treatment until symptoms resolve to $\leq$ Grade 1. 
 
Consider reinitiating MLN0128 treatment with a dose reduction. (a)
 
If toxicity recurs at Grade 3, discontinue MLN0128 treatment.
 

4	Life-threatening: Ventilatory support indicated	Rule out infection and consider treatment with corticosteroids.	Discontinue MLN0128 treatment.

QD $\times$ 5D=once daily for 5 days each week.

(a) Phase 1b Part 1 cohorts: for patients receiving a starting dose of 5 mg, reduce by 20% (to 4 mg). If dose modification is required for patients receiving  $\leq$ 4 mg QD, then the frequency of dosing should be decreased to QD $\times$ 5D, rather than decreasing the daily dose administered. For all other patients: the initial dose reduction should be from 4 mg to 3 mg, with further reduction to 2 mg if necessary.

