## **MLN0128**

### **Clinical Study Protocol C31001 Amendment 6, EudraCT: 2014-001921-34**

decreasing the daily dose administered. If study drug dosing is delayed for more than 14 consecutive days for MLN0128-related toxicity, despite supportive treatment per standard clinical practice, or more than 2 dose reductions of MLN0128 are required, the patient will be discontinued from the study.

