### **6.3 Dose-Modification Guidelines for the Phase 2 Portion of the Study**

#### **6.3.1 Dose Modification or Treatment Delay for MLN0128-Related Toxicity**

Based on the outcome of a safety and tolerability analysis performed in the phase 1b portion of the study, MLN0128 4 mg QD in combination with either exemestane or fulvestrant was determined as the phase 2 starting dose. Another safety and tolerability assessment will be performed during the phase 2 portion of the study where the first 6 patients treated with MLN0128 4 mg QD in combination with exemestane or fulvestrant who have completed 2 cycles of treatment with MLN0128 will be evaluated for TEAEs. Enrollment of patients into the study will continue during this safety and tolerability assessment.

In addition, during the phase 2 portion of the study, both tolerability and need for dose reductions and/or modifications will continue to be monitored for all patients in all cycles. If, based on this assessment, the 4 mg QD starting dose identified in Part 2 of the phase 1 portion is deemed unfavorable, in conjunction with agreement of the study investigators and the medical monitor, the starting dose may be adjusted to 2 or 3 mg QD for all newly enrolled patients to improve long-term tolerability. Patients who were enrolled at 3 or 4 mg QD in Part 2 of the phase 1 portion and the phase 2 portion will be maintained at this dose unless dose modifications are required due to individual tolerability. A starting dose reduction, if required, will be documented to all study sites by formal written communication.

MLN0128 administration should be withheld for MLN0128-related toxicities that are  $\geq$ Grade 3 despite supportive treatment per standard clinical practice. If the event resolves to Grade 1 or baseline values within 2 weeks of interrupting treatment, the patient may resume study treatment at a 25% to 50% dose reduction (ie, 2 mg QD). Alternatively, if dose modification is required for patients receiving 2 mg QD, then the dosing frequency should be decreased to 5 days per week instead of decreasing the daily dose administered. If MLN0128 dosing is delayed for more than 14 consecutive days for MLN0128-related toxicity despite supportive treatment per standard clinical practice, or more than 2 dose reductions of MLN0128 are required in a patient, stop MLN0128 therapy, discontinue the patient from the study, and complete the EOT visit within 30 to 40 days after the last dose of

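### Table 6-6 allows a 4-week MLN0128 hold for related Grade 2 pneumonitis, while the 14-day sentence in Protocol 6.3.1 (and, less clearly, in 6.2) read literally ends treatment sooner

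*Protocol*

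**What the plan says.** Protocol Table 6-6, in its Grade 2 row, interrupts MLN0128. When symptoms fall to Grade 1 or lower, the instruction is to "reinitiate MLN0128 treatment with a dose reduction". The outer limit is "If no recovery within 4 weeks, then discontinue MLN0128 treatment".

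Protocol Section 6.3.1, which covers dose modification in phase 2, has its own time limit: "If MLN0128 dosing is delayed for more than 14 consecutive days for MLN0128-related toxicity despite supportive treatment per standard clinical practice". The consequence is to "stop MLN0128 therapy, discontinue the patient from the study".

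Protocol Section 6.2, which covers phase 1b, is worded similarly: "If study drug dosing is delayed for more than 14 consecutive days for MLN0128-related toxicity", despite supportive treatment, then "the patient will be discontinued from the study".

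Section 6.3.1 also ends with a requirement to contact the sponsor's project clinician before any MLN0128 dose modification in any patient.

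**The concern.** The 14-day sentences refer to MLN0128-related toxicity in general. They name no grade and make no exception for pneumonitis. Table 6-6 gives one grade of one such toxicity twice as long. A patient with related Grade 2 pneumonitis who recovers in the third or fourth week of a hold is restarted under the table and discontinued under the literal general rule. Nothing in the protocol says whether the Section 6.7 tables or Sections 6.2 and 6.3.1 govern.

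What is at stake first is safety and consistency of exposure: whether a patient is re-exposed to MLN0128 after pneumonitis should not depend on which page a site consults, and about 40 centers in three countries are planned. The primary phase 2 endpoint may also be touched. SAP Section 7.8.1 requires stable disease at the end of Cycle 2 and again at the end of Cycle 4 for a patient with a best response of stable disease to count toward CBR-16. A patient off treatment no longer follows the cycle-based scan schedule.

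**Working it through.** No sample size, power or error rate is involved. The check sets the passages side by side, with simple day counts.

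**Hold length.** Table 6-6 limit: 4 × 7 = 28 days. Sections 6.2 and 6.3.1 limit: 14 days, with discontinuation beyond that. Difference: 28 − 14 = 14 days.

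| Related Grade 2 pneumonitis | Table 6-6 | 14-day sentence, read literally |
|---|---|---|
| Recovery by day 14 of the hold | Restart, reduced dose | Limit not reached |
| Recovery on days 15 to 28 | Restart, reduced dose | Discontinue |
| No recovery by day 28 | Stop MLN0128 | Already discontinued |

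The two disagree on whether to restart only in the middle row. Events judged unrelated to MLN0128 fall outside the 14-day sentences.

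**The other Section 6.7 tables.** Tables 6-1 (hyperglycemia) and 6-4 (rash) use a 2-week limit, in rows for Grade 3 or higher only. The Grade 2 rows of Tables 6-2 (hyperlipidemia) and 6-3 (oral mucositis) allow a hold until recovery and state no limit. Table 6-6 is the only management table that states a limit longer than 2 weeks, and nothing marks it as a deliberate exception.

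**Consequence.** Table 6-6 ends MLN0128 treatment. Sections 6.2 and 6.3.1 take the patient off study. Section 7.7 keeps patients who stop MLN0128 for reasons other than progression in the study for posttreatment assessments. The passages therefore differ on what is stopped as well as when.

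**Endpoint illustration.** Assume a hold that begins on Cycle 3 Day 1 and a cycle calendar that runs on during the hold.

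- Cycle 3 Day 1 = 2 × 28 + 1 = study day 57.
- A 14-day hold covers days 57 to 70; a longer one triggers discontinuation under Section 6.3.1.
- A 28-day hold covers days 57 to 84, which Table 6-6 permits.
- Cycle 4 Day 28 = 4 × 28 = day 112.

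Under Table 6-6 the day-112 scan can still take place on treatment. Under Section 6.3.1 the patient is off treatment by then, and the Schedule of Events moves posttreatment imaging to every 3 months, so a scan at day 112 is no longer scheduled. This shows that an effect on CBR-16 can occur. It does not show how often.

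**The case against.** The strongest reply is that the passages can be read together. In Section 6.3.1 the 14-day sentence closes a paragraph that opens with "MLN0128 administration should be withheld for MLN0128-related toxicities that are" Grade 3 or higher, and then describes recovery within 2 weeks. In Section 6.2 it closes a paragraph on adverse events that meet the DLT definition. Grade 2 pneumonitis is not a Grade 3 event, and it would be a DLT only by another route, such as too few Cycle 1 doses given. The placement of the 2-week limits in Tables 6-1 and 6-4 fits this reading. Table 6-6 is also the only pneumonitis-specific instruction, added by Amendment 3, so a site might naturally treat it as the specific rule. Finally, a Table 6-6 restart involves a dose reduction and so triggers contact with the project clinician.

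Much of this stands. It is strong for Section 6.2 and weaker for Section 6.3.1, where neither the sentence nor its heading carries a grade limit. The same sentence caps dose reductions at two without saying whether a Grade 2 pneumonitis reduction counts. Section 6.7.6 presents Table 6-6 as guidance, so a site could rank the two either way. Contact with the project clinician makes silent divergence less likely, but it yields case-by-case answers instead of a written rule.

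A reader might also infer that patients stopped under the 14-day rule will usually lose their CBR-16 status. The documents do not support that. The unconfirmed definition counts a complete or partial response at any time, and the confirmed definition counts a confirmed one at any time, so responders are largely unaffected. The protocol calls for further imaging in patients who stop without radiographic progression, and Section 7.7 keeps them under assessment.

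**Conclusion.** This is an internal inconsistency that should be corrected, and it is narrow. It concerns MLN0128-related Grade 2 noninfectious pneumonitis with a hold of 15 to 28 days, chiefly between Table 6-6 and Section 6.3.1 and less clearly between Table 6-6 and Section 6.2. It rests on reading the 14-day sentences as written; a context-limited reading is reasonable, but no passage states it.

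A reader might take this as an unavoidable contradiction affecting every Grade 2 pneumonitis case. The text does not go that far: shorter holds and unrelated events are unaffected, and a site could reconcile the passages from context. The number of affected patients could be zero, since the documents give no pneumonitis rate. An effect on CBR-16 or on the interim counts is possible for patients whose best response is stable disease, but it cannot be sized. The case for correction rests mainly on patient safety and uniform handling.

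**What to change.** The sponsor should reconcile Table 6-6 with Sections 6.2 and 6.3.1 so that one maximum interruption applies to related Grade 2 pneumonitis. One further sentence should state whether the Section 6.7 tables or the general rule govern hold length, and whether the 14-day sentences are confined to Grade 3 or higher events or DLTs. The same edit should align the consequence, treatment stop or study discontinuation, with Section 7.7. Which limit applies is a clinical decision for the sponsor, and this review takes no position on it. The cost is a few sentences in the next amendment or a site letter, with no change to sample size, data collection or analysis.

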### 6.8 Blinding and Unblinding

This is an open-label study.

### 6.9 Description of Investigational Agents

MLN0128 will be supplied as capsules for oral administration. MLN0128 is available in 3 dose strengths, 1 mg, 3 mg, and 5 mg, each containing 1 mg, 3 mg, and 5 mg of MLN0128, respectively, in addition to the following inactive ingredients: microcrystalline cellulose (solid filler/diluents), magnesium stearate (lubricant), and hard gelatin capsule.

All 3 dose strengths are formulated into size 2 capsules, and each dose strength is differentiated by color, as listed below:

- 1 mg MLN0128 capsules: white opaque color.

## **MLN0128**

### **Clinical Study Protocol C31001 Amendment 6, EudraCT: 2014-001921-34**

- 3 mg MLN0128 capsules: Swedish orange opaque color.
- 5 mg MLN0128 capsules: gray opaque color.

The original MLN0128 capsules based on unmilled API will continue to be supplied to support treatment for ongoing patients in Part 1 of the phase 1b portion of the study. The new MLN0128 capsules based on milled API will be administered to patients in Part 2 of the phase 1b and the phase 2 portions of the study.

Exemestane is a commercially available oral drug supplied as tablets.[39] Fulvestrant is a commercially available drug administered as an IM injection.[40]

#### **6.10 Preparation, Reconstitution, and Dispensation**

MLN0128 will be provided in 60-cc high-density polyethylene (HDPE) bottles with polypropylene, child-resistant caps and induction seal. MLN0128 will be dispensed with dosing instructions for home use, including the requirement that capsules are stored in their original containers and that capsules be swallowed whole and not opened, chewed, or manipulated in any way. Materials provided by the sponsor should be dispensed to patients with clear administration instructions from the investigator.

MLN0128 is an anticancer drug and, as with other potentially toxic compounds, caution should be exercised when handling MLN0128 capsules.

#### **6.11 Packaging and Labeling**

MLN0128 will be provided by Millennium and will be handled at the investigative site as open-label material. MLN0128 capsules are packaged in 60-cc HDPE bottles with polypropylene, child-resistant caps and induction seal. For all 3 dose strengths, each bottle contains 30 capsules and will have a label containing pertinent study information, country-specific requirements, and a caution statement.

Supplies of the new MLN0128 capsules based on milled API will be accompanied with a new label to differentiate them from the existing supplies of the MLN0128 capsules that are based on unmilled API.

While the patient is enrolled in the study, exemestane and fulvestrant may be supplied either by the site from commercial sources (US sites) or provided by Millennium (ex-US sites). When provided by Millennium, exemestane and fulvestrant will be appropriately labeled in compliance with local and regional regulations.

**6.12 Storage, Handling, and Accountability**

Upon receipt at the investigative site, MLN0128 should be stored in the original bottles until use and stored at room temperature from 15°C to 30°C (59°F to 86°F). All temperature excursions will be reported to the sponsor for assessment and authorization for continued use. All investigational supplies must be stored in a secure area with controlled access and will be stored in original packaging. All MLN0128 should be used before the retest expiry date.

A drug dispensing log, including records of drug received from the sponsor and drug dispensed to the patients, will be provided and kept at the study site. Storage area temperature conditions must be monitored and recorded daily. A daily temperature log will also be kept at the study site.

Because MLN0128 is an investigational agent, it should be handled with due care. In case of contact with broken capsules, raising dust should be avoided during the clean-up operation. The product may be harmful if inhaled, ingested, or absorbed through the skin. Gloves and protective clothing should be worn during the clean-up operation. The area should be ventilated and the spill site washed after material pick-up is complete. The spilled material should be disposed of as hazardous medical waste in compliance with federal, state, and local regulations. In case of contact with the powder (eg, from a broken capsule), skin should be washed immediately with soap and copious amounts of water for at least 15 minutes. In case of contact with the eyes, copious amounts of water should be used to flush the eyes for at least 15 minutes. Medical personnel should be notified.

Patients will receive instructions for home storage and administration of MLN0128. Patients will also receive diary cards to record dosing compliance of MLN0128, the appropriate combination therapy (exemestane or fulvestrant), and instructions for their completion.

Patients will be instructed to return any unused study drug in the original packaging along with their completed diary cards at the appropriate visits.

Please refer to the Study Manual for additional instructions.

Exemestane and fulvestrant should be stored according to instructions provided in the manufacturer's most recent package insert or SmPC.

## **7. STUDY CONDUCT**

This trial will be conducted in compliance with the protocol, Good Clinical Practice (GCP), applicable regulatory requirements, and International Conference on Harmonisation (ICH) guidelines.

### **7.1 Study Personnel and Organizations**

The contact information for the Millennium Study Monitor for this study, the central laboratory and any additional clinical laboratories, and other third-party vendors may be found in the Study Manual. A full list of investigators is available in the sponsor's investigator database.

### **7.2 Arrangements for Recruitment of Patients**

Recruitment and enrollment strategies for this study may include recruitment from the investigator's local practice or referrals from other physicians. If advertisements become part of the recruitment strategy, they will be reviewed by the institutional review board (IRB)/independent ethics committee (IEC). It is not envisioned that prisoners (or other populations that might be subject to coercion or exploitation) will be enrolled into this study.

### **7.3 Treatment Group Assignments**

For Part 1 of the phase 1b portion of the study, all enrolled patients will be assigned to receive MLN0128 capsules based on unmilled API at 5 mg QD in combination with either fulvestrant or exemestane, at the same dose previously administered.

For Part 2 of the phase 1b portion of the study, the first 6 patients (Cohort 1) will be assigned to receive MLN0128 capsules based on milled API at 3 mg QD with either exemestane or fulvestrant, at the same dose previously administered. Based on safety and tolerability assessments of Cohort 1, an additional 6 patients (Cohort 2) will then be assigned to receive MLN0128, at either 4 or 2 mg QD, in combination with either exemestane or fulvestrant.

Enrollment in the phase 2 portion of the study will commence for patients on MLN0128 in combination with exemestane or fulvestrant therapy once the safety assessment has been completed for the phase 1b portion of the study.

Additional details regarding treatment cohorts are provided in Section [4.1](#).

## 7.4 Study Procedures

Refer to the [Schedule of Events](#) for timing of assessments. Additional details are provided as necessary in the sections that follow.

### 7.4.1 Informed Consent

Each patient must provide written informed consent before any study-required procedures are conducted, unless those procedures are performed as part of the patient's standard care.

### 7.4.2 Patient Demographics

The date of birth, race, and ethnicity of the patient are to be recorded during Screening.

### 7.4.3 Medical History

During the Screening period, a complete medical history will be compiled for each patient. The history will emphasize the background and progress of the patient's malignancy and include a description of prior therapies for the disease. In addition, concomitant medications will be recorded as specified in Section [7.4.10](#).

For patients enrolling into phase 2 (only) who have measurable disease and are undergoing CT scans (rather than MRIs) for tumor assessment, the most recent CT scan performed before their baseline CT scan in this study will be collected, if available, and forwarded to a third-party vendor for tumor volume/size analysis (see Section [8.1.7.3](#)). The date of the scan should be indicated, if known. Availability of the scan is not a prerequisite for study eligibility.

### 7.4.4 Physical Examination

A physical examination will be completed per standard of care at the times specified in the [Schedule of Events](#).

### 7.4.5 Patient Height and Weight

Height will be measured only during Screening. Weight will be measured at the times specified in the [Schedule of Events](#).

### 7.4.6 Vital Signs

Vital signs will be assessed at the times specified in the [Schedule of Events](#).

#### **7.4.7 ECOG Performance Status**

The ECOG performance status (refer to Section [14.1](#)) will be assessed at the times specified in the [Schedule of Events](#).

#### **7.4.8 MUGA Scan or ECHO**

A MUGA scan or ECHO will be administered at the time points specified in the [Schedule of Events](#).

#### **7.4.9 Pregnancy Test**

Pregnancy testing will not be performed in this study as enrollment is restricted to postmenopausal women only.

#### **7.4.10 Concomitant Medications and Procedures**

Medications used by the patient and therapeutic procedures completed by the patient will be recorded in the eCRF from first dose of MLN0128 through 30 days after the last dose. See Section [6.4](#) and Section [6.5](#) for a list of medications and therapies that are prohibited and/or permitted during the study.

#### **7.4.11 AEs**

Monitoring of AEs, serious and nonserious, will be conducted throughout the study as specified in the [Schedule of Events](#). Refer to Section [9](#) for details regarding definitions, documentation, and reporting of pretreatment events, AEs, and SAEs.

#### **7.4.12 Enrollment**

A patient is considered to be enrolled in the study when the first dose of MLN0128 is administered. Procedures for completing the enrollment information are described in the Study Manual.

#### **7.4.13 ECG**

A single, 12-lead ECG will be administered at the time points specified in the [Schedule of Events](#) and in the [Phase 1b Pharmacokinetic and ECG Sample Breakdown](#) and the [Phase 2 Pharmacokinetic and ECG Sample Breakdown](#) table. Additional ECGs may be obtained as clinically indicated.

#### **7.4.14 Clinical Laboratory Evaluations**

Clinical laboratory evaluations will be performed locally. Handling and shipment of clinical laboratory samples will be outlined in the Study Manual and/or laboratory manual. Clinical laboratory evaluations will be performed as outlined below.

##### **Clinical Chemistry, Hematology/Coagulation, and Urinalysis**

Blood samples for analysis of the following clinical chemistry and hematological parameters and urine samples for urinalysis will be obtained as specified in the [Schedule of Events](#).

Results of hematology and clinical chemistry safety labs must be available and reviewed by the investigator before enrollment and initial administration of MLN0128.

##### **Hematology/Coagulation**

A blood sample for complete blood count with platelet count and white blood cell (WBC) count with differential will be obtained at the times specified in the [Schedule of Events](#).

The hematology and coagulation panels include the following:

- Hemoglobin
- Hematocrit
- Platelet (count)
- Leukocytes with differential
- Neutrophils (ANC)
- Activated partial thromboplastin time (aPTT)
- Prothrombin time/international normalized ratio (PT/INR)

